3.1. SAMPLE SIZE AND POWER

Results from published clinical trials of PSC patients including Zhu et al., 2015 and Fickert et al., 2017 were reviewed. These publications were used along with consideration of inclusion and exclusion criteria for this study to estimate mean Baseline ALP and to estimate variability. Total sample size was chosen based on balancing consideration of business costs, time to enroll subjects with this rare disease and the mean change which could be detected given the mean Baseline and variability assumptions. The standard deviation for change from Baseline in ALP was assumed to be 200. A total of 90 subjects, 30 subjects per group, is sufficient to detect a mean difference from placebo within a dose group of 147 with 80% power at an alpha of 0.05. Assuming a mean Baseline ALP of 450, this equates to a 32.7% reduction. This study should be adequate to determine if there is a positive signal in ALP during HTD1801 treatment.

While the sample size was originally planned to be 90 subjects, in view of the protracted period necessary to enroll subjects into the study, a strategy session in the fall of 2018 with external consultants advised that the study would be adequately powered by enrolling approximately 60 subjects. Specifically, it was determined that a total of 63 subjects, 21 subjects per group, would be sufficient to detect a mean difference of 180 for each dose group vs. placebo with 80% power for a two-sided t-test with alpha of 0.05. A protocol amendment was deemed unnecessary.

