CONFIDENTIAL

CLINICAL PROTOCOL

TITLE OF STUDY:

A Proof-of-Concept and Dose-Ranging Study Investigating the Efficacy and Safety of HTD1801 in Adult Subjects with Primary Sclerosing Cholangitis (PSC)

Protocol HTD1801.PCT003

Trial Registration: NCT03333928

Date of issue: 07 January 2019

Version number: 1.4PK

Sponsor: HighTide Biopharma Pty. Ltd.

[name],

[name]

Australia

Signatures of Approval of Protocol (Version 1.4PK)

This protocol was subject to critical review and has been approved by the following persons:

Affiliation	Name	Signature	Date:
Sponsor:	[name]		
Statistician:	[name], MS		
Medical Monitor:	[name]		

Sponsor: HighTide Biopharma Pty. Ltd.

[name],

[name]

Australia

Sponsor Contact: [name]

HighTide Biopharma Pty, Ltd.

[contact]

E-mail: [contact]

Medical Monitor: [name], PhD, JD

Clinical Research Physician

Cato Research

[name]

[name] USA [contact] [contact]

E-mail: [contact]

STUDY SYNOPSIS

Name of sponsor company: HighTide BioPharma Pty. Ltd.

Name of finished product: HTD1801 Tablets

Name(s) of active ingredient(s): Berberine Ursodeoxycholate (HTD1801)

Title of study: A Proof-of-Concept Study Investigating the Efficacy and Safety of HTD1801 in Adult Subjects with Primary Sclerosing Cholangitis (PSC)

Investigator(s): TBD

Number of sites: TBD

Study period: 18 weeks Phase of development: 2

Objectives:

The primary objective of this proof-of-concept study is to evaluate the effects of HTD1801 on alkaline phosphatase (ALP) in adult subjects with PSC.

The secondary objectives of this study are to evaluate the effects of HTD1801 on concurrent disease activity of inflammatory bowel disease (IBD), and on the safety and tolerability of HTD1801 over 18 weeks in adult subjects with PSC.

Pharmacokinetic (PK) and pharmacodynamics (PD) objectives include:

- Develop and validate population PK models for the components of HTD1801: berberine (BBR) and ursodeoxycholic acid (UDCA);
- Calculate individual single-dose and steady-state exposure metrics based on non-compartmental analysis methods in adult patients with PSC;
- Evaluate exposure-response models for efficacy;
- Evaluate the relationship between exposure, adverse events, and serious adverse events.

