9.4 PROTOCOL COMPLIANCE

Substantive changes in the protocol include changes that affect the safety of subjects or changes that alter the scope of the investigation, the scientific quality of the study, the experimental design, dosages, assessment variable(s), the number of subjects treated, or the subject-selection criteria. Such changes must be prepared as a protocol amendment by the sponsor and implemented only upon joint approval of the sponsor and the investigator. A protocol amendment must receive IRB/IEC approval before implementation. In parallel with the IRB/IEC approval process, the protocol amendment will be submitted to the appropriate regulatory authority as an amendment to the regulatory submission under which the study is being conducted. If a protocol amendment requires changes in the informed consent form, the revised informed consent form prepared by the investigator must also be approved by the sponsor, study monitor, and the IRB/IEC before implementation.

Departures from the protocol are allowed only in situations that eliminate an immediate risk to a subject and that are deemed crucial for the safety and well-being of that subject. The investigator or the attending physician also will contact the medical monitor as soon as possible in the case of such a departure. These departures do not require preapproval by the IRB/IEC; however, the IRB/IEC and medical monitor must be notified in writing as soon as possible after the departure has been made. In addition, the investigator will document in the subject's eCRF the reasons for the protocol deviation and the ensuing events.

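### Does cutting the planned sample from 90 to about 60 without a protocol amendment call for a change to the statistical plan?

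*SAP*

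**What the plan says.** SAP 3.1 gives the calculation for 90 subjects and then reports that "a strategy session in the fall of 2018 with external consultants advised that the study would be adequately powered by enrolling approximately 60 subjects". It continues that "it was determined that a total of 63 subjects, 21 subjects per group, would be sufficient to detect a mean difference of 180". That calculation compares either dose with placebo, at 80% power and a two-sided test at 0.05. The reason given is the long time needed to enrol. The paragraph closes with "A protocol amendment was deemed unnecessary". SAP 1.1 adopts the figure of about 60.

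Protocol 9.4 describes which changes are substantive. Its list includes "the experimental design, dosages, assessment variable(s), the number of subjects treated, or the subject-selection criteria". It then says: "Such changes must be prepared as a protocol amendment by the sponsor and implemented only upon joint approval of the sponsor and the investigator", and "A protocol amendment must receive IRB/IEC approval before implementation".

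The protocol gives its own number in three places. The synopsis plans 90 in total. Section 8.2.7 has 30 per group, with 80% power for a difference of 147. Section 3.2 words 90 as the most that will be enrolled. The title page carries "Date of issue: 07 January 2019", which is after the 2018 session.

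**The concern.** Set beside Protocol 9.4, the SAP seems to record in its own words that a mandatory step was skipped. The timing adds to this: a new protocol version was issued after the decision, and its synopsis and section 8.2.7 still plan 90.

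The cut is also not small. It removes about a third of the planned subjects, and the claim of adequate power holds only against a larger difference than the protocol's. A reader could fear three things: that the approved protocol described a more sensitive trial than the one run, that the power statement is wrong, or that the sample size was reset with knowledge of the results. Any of these could bear on how far the primary comparison can be trusted.

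**Working it through.** **Inputs.** SD of change in ALP is 200 and mean baseline ALP is 450 (Protocol 8.2.7, SAP 3.1). Alpha is 0.05 two-sided, allocation is 1:1:1, and neither calculation includes an allowance for dropout. The SAP does not restate the SD for the 63-subject calculation, so 200 is assumed to carry over.

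**Method.** Two-sample t-test with n per group. The standard error of the difference is SE = 200 × √(2/n), the noncentrality is difference/SE, and the degrees of freedom are 2n − 2. Power is read from the noncentral t distribution.

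**The plan's own figures.**

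- n = 30, difference 147: SE = 200 × √(2/30) = 51.6; noncentrality 147/51.6 = 2.85; power 79.9%. The stated 80% is reproduced.
- n = 21, difference 180: SE = 200 × √(2/21) = 61.7; noncentrality 180/61.7 = 2.92; power 81.2%. The stated 80% is reproduced.

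**What the cut costs.**

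| Subjects (per group) | Power for 147 | Power for 180 | Difference detectable with 80% power | As % of 450 |
|---|---|---|---|---|
| 90 (30) | 79.9% | 92.9% | 147.1 | 32.7% |
| 63 (21) | 64.2% | 81.2% | 177.2 | 39.4% |
| 60 (20) | 62.0% | 79.2% | 181.8 | 40.4% |

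The stated difference of 180 is 180/450 = 40.0% of baseline, against 147/450 = 32.7%. The sample falls by 30% (63/90 = 0.70) or 33% (60/90 = 0.67). The standard error of a pairwise difference grows by 61.7/51.6, about 1.20.

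These powers are unadjusted. Two factors that the documents do not quantify move them in opposite directions at 63 subjects. If baseline ALP and its change correlate at an assumed 0 to 0.5, with SD = 200 × √(1 − r²), power for 147 runs from 64% to 77%. If an assumed 0 to 20% of Week 6 values are missing, it runs from 64% to 54%.

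**What 147 and 180 are.** Protocol 8.2.7 and SAP 3.1 say the size was chosen by weighing cost, time to enrol and the change that could be detected. Neither document offers 147 as a clinically required effect. It is what 30 per group can detect, and 180 is about what 21 per group can detect (177.2). The smaller sample by itself accounts for the larger difference.

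**The texts side by side.** Protocol 9.4 governs substantive changes to the protocol. Enrolling about 60 stays within the ceiling in Protocol 3.2, so the sponsor can argue that this text did not change. The synopsis and 8.2.7 point the other way, since they state 90 as the plan, and 9.4 makes no exception for reductions. The protocol is therefore ambiguous between a ceiling and a target, and SAP 3.1 does not say which reading it relied on.

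**What depends on the planned N.** The primary analysis in SAP 5.2.2 is a repeated-measures model adjusted for baseline ALP, IBD diagnosis and UDCA status. It reports differences with 95% confidence intervals. Its model terms, alpha and comparisons do not use the target sample size. Lower precision will appear directly as wider intervals.

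**The case for a change.** The strongest case for acting is that Protocol 9.4 is explicit. Slow enrolment is not a ground it recognises for going without an amendment, and the SAP neither cites the ceiling in Protocol 3.2 nor gives any other basis for its statement. The protocol version issued after the session could have carried the new number and did not. SAP section 7, which records changes, lists only endpoints. The COVID-19 stop in March 2020 came later and does not explain the decision. All of this stands: the documents do not show how the cut was squared with 9.4, and adequate power is true only for a difference near 180.

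Other arguments carry less weight. The sentence "Departures from the protocol are allowed only in situations that eliminate an immediate risk to a subject" sits in a paragraph about individual subjects: it speaks of that subject's safety, of the attending physician and of the subject's case report form. It does not govern a sponsor's decision on sample size. Effects on consent forms, or on what ethics committees were told, cannot be judged, because those records are not in the two documents. Appendix A asks only for an approximate number.

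Nothing in the text suggests that ALP by arm was seen. The one unblinded check described in SAP 3.2 followed the session and concerned the distribution of UDCA users. SAP 3.4 plans only a final analysis plus safety oversight by the DSMB.

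**Conclusion.** The conflict between SAP 3.1 and Protocol 9.4 is genuine, but it is a matter of approval and record-keeping. It is not a flaw in the statistical plan. Both sample-size statements are correct for their own N. SAP 3.1 already discloses both sizes, both detectable differences, the reason, the season and forum of the decision, and the absence of an amendment.

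The cost is a fall in unadjusted power for 147 from 79.9% to about 62–64%, with standard errors about 20% larger, assuming the SD of 200 holds and no data are missing. For a proof-of-concept study in a rare disease that was enrolling slowly, that is a fair trade-off made in the open.

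Further wording in the SAP would alter no enrolment, since recruitment ended on 25 March 2020, and no model, test or interval. Whether the IRB/IEC was informed, and on what reading of 9.4, should be settled in the trial file and can be stated in the study report. This conclusion rests on the two documents alone; approvals held elsewhere could confirm or refute the sponsor's reading without affecting the analysis.

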3.2. RANDOMIZATION AND BLINDING

Period 1: Placebo- and dose-controlled, parallel-group period

Subjects will be enrolled in equal numbers to one of the initial three treatment groups (placebo BID, HTD1801 500 mg BID, HTD1801 1000 mg BID) during the initial 6-week, double-blind, placebo- and dose-controlled, parallel-group period. Randomization will be centrally controlled, stratified

according to a co-existing diagnosis of IBD and UDCA status, and subjects will be assigned a pre-packaged and numbered treatment.

Subjects who were currently taking ursodeoxycholic acid (UDCA), or who had taken UDCA during the 6 weeks prior to randomization were to have completed a 6-week washout period before Baseline measurements per Protocol Version 1.2 dated 01 February 2018. The UDCA restriction was modified in Protocol Version 1.3 dated 12 June 2018 since only one subject had been enrolled in the earlier version of the protocol. Subjects on UDCA were eligible as long as the dose of UDCA was stable for at least 6 weeks prior to the Baseline visit.

Following the strategy session in the fall of 2018, an unblinded individual from the CRO, Cato Research, was tasked with determining whether the number of subjects taking UDCA was evenly distributed among the three study groups. This was found not to be so, with one dose cohort having no subjects who had previously been taking UDCA. While at the onset of the study, Period 1 randomization was stratified only by IBD diagnosis, this discovery spurred the inclusion of UDCA status as a stratification factor in an attempt to ensure even distribution between treatment groups for the primary analysis. UDCA status was therefore retroactively applied as a stratification factor to those 42 subjects who had already been randomized to Period 1, and gaps in these new strata were subsequently filled by 17 subjects enrolling from that point forward, with new randomization blocks prospectively added.

This new manual randomization process was initiated in November 2019. The autogenerated randomization process in the web-response system was too time consuming and costly to implement. This is managed by [name] (Boston Biostatistics Research Foundation, Inc.) in conjunction with an unblinded data base administrator, [name] (Cato Research Limited). The additional stratification factor of UDCA status will be included in the modeling.

Period 2: Dose-controlled extension

Following their completion of Period 1, subjects will enroll in a 6-week extension period in which subjects previously randomized to 500 mg or 1000 mg BID will continue for 6 more weeks at that previous dose, while subjects previously randomized to placebo will be randomly assigned to receive 6 weeks of either 500 mg or 1000 mg BID.

Period 3: Randomized withdrawal

Following their completion of Period 2, subjects will enroll into a 6-week randomized withdrawal period in which all subjects will be randomly assigned in a 1 to 1 ratio to either continue on the active treatment they received in Period 2, or be assigned to placebo so that 50% of the subjects remain on the experimental treatment at the previous dose, and 50% will receive placebo.

All subjects and study personnel will remain blinded as to the treatment administered throughout the study with the exception of an unblinded statistician who will develop the randomization list with the expanded strata and an unblinded EDC designer who will load the completed randomizations

into the EDC system. All study test drug will be provided in matching white tablets, four to a bottle, two bottles to be administered each day, one in the morning and one in the evening. A 45-day supply will be provided to each subject at each visit to cover the next 6-week period with an additional 3 days of coverage to provide for possible scheduling conflicts.

In this double-blind study, if a medical emergency occurs and a decision about a subject's condition requires knowledge of the treatment assignment in order to properly treat the subject, the study blind may be broken for that specific subject only. Ideally, the decision to break the blind for this one subject should only be made after consultation with the Medical Monitor or Sponsor Representative.

Any broken blind must be clearly justified and explained by a note in the subject's source documents.

3.3. HANDLING OF DATA

3.3.1. Strata and Covariates

Statistical models run for the primary endpoint as well as secondary continuous endpoints in Period 1 will include IBD diagnosis as randomized and UDCA status when entering the study as covariates. Secondary continuous endpoints in Periods 2 and 3 will also include IBD diagnosis and UDCA status as a covariate.

3.3.2. Examination of Subject Subsets

Analysis of the primary endpoint will additionally be presented by IBD diagnosis as randomized and UDCA status when entering the study.

3.3.3. Multiple Testing and Comparisons

All analyses will be conducted without adjustments for multiple comparisons for this proof-of-concept study.

3.3.4. Missing Data

Every effort will be made to obtain required data at each scheduled evaluation from all subjects who have been treated. Missing end dates for dosing in each period will be imputed using the first date of dosing in the next period if available, or the last collected visit date for the period if not. Missing start dates will be imputed as the earliest study drug dispensation date for the period, provided there is a last dose date or multiple dispensations in the period. No other imputations will be used for this analysis except for handling of incomplete dates.

3.3.5. Imputation of Incomplete Dates

An incomplete date is any date for which either the day, month, or year is unknown, but all three fields are not unknown. An incomplete date occurs when the exact date an event occurred or ended cannot be obtained from a subject. For many of the analyses, a complete date is necessary in order

to determine if the event should be included in the analysis (i.e., if the event is treatment-emergent) or to establish the duration of an event. In such cases, incomplete dates will be imputed.

For purposes of imputation, all events with an incomplete end date are assumed to have ended on or before the day the form was completed. In an effort to minimize bias, the project statistician will impute dates in a systematic but reasonable manner, as described below.

For event start dates, if the month/year is the same as the Day 1 month/year then the date will be set to the date of Day 1. In other cases, missing days will be imputed as the day component of Day 1; missing months/years will be imputed as the month/year of Day 1. If the end date is present, then the imputed start date will be set to the end date if the above imputation imputes a date after the end date.

For event end dates, if the month/year is the same as the event start date month/year then the date will be set to the date of the event start date. In other cases, missing days will be imputed as the day component of the event start date, or if missing, then the day component of the treatment start date; missing months/years will be imputed as the month/year of the event start date, or if missing then the months/years of the treatment start date.

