5.3. SAFETY

5.3.1. Adverse Events

AEs will be mapped to a Medical Dictionary for Regulatory Activities (MedDRA) version 20.1 preferred term (PT) and system organ classification (SOC). If a subject experiences multiple events that map to a single preferred term, the greatest severity grade according to the Common Terminology Criteria for Adverse Events (CTCAE) Version 4.0 will be assigned to the preferred term for the appropriate summaries. Should an event have a missing severity or relationship, it will be classified as having the highest severity and/or assumed related to study medication. The overall occurrence of any TEAEs, TEAE related to study drug, severe TEAEs, serious TEAEs, TEAE leading to discontinuation of study drug, and TEAE leading to death, alongside individual counts of each respective TEAE. The occurrence of TEAEs will be summarized by treatment group by SOC, and PT based on the treatment taken at AE start date. Summaries of the total number of subjects receiving each treatment and the average weeks of exposure for each treatment will be provided for context.

Separate summaries of each TEAE by period, TEAEs leading to the discontinuation of study, TEAEs related to study drug, and serious TEAEs will be generated and summarized by SOC and PT. The occurrence of TEAEs will be summarized by treatment group by SOC, PT, and Severity will also be summarized.

All adverse events reported will be listed for individual subjects showing verbatim term, PT and SOC. All AEs that occurred prior to the initiation of study treatment will be excluded from the tables but will be included in the listings.

Missing onset dates will be imputed as previously outlined in [Section 3.3.5](#) as required to determine treatment-emergent events.

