5.3.3. Concomitant Medications

Previous and concomitant medications will be coded using the World Health Organization (WHO) Drug Dictionary Enhanced September 2017 version. Previous and concomitant medications will be presented in a data listing. Concomitant medications will additionally be summarized by aggregate treatment group.

Missing end dates will be imputed as previously outlined in [Section 3.3.5](#) as required to determine concomitant medications, and all ongoing medications will be considered concomitant.

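### The SAP's partial-date rule, taken literally, can give impossible, pre-dose, off-study or wrong-period AE start dates and end dates that are too early (minor).

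*SAP*

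**What the plan says.** SAP 3.3.7 defines Day 1 as the first day of study drug in Period 1. SAP 3.3.5 then completes partial dates as follows.

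- **Start, same month and year as Day 1:** "if the month/year is the same as the Day 1 month/year then the date will be set to the date of Day 1".
- **Start, all other cases:** "missing days will be imputed as the day component of Day 1; missing months/years will be imputed as the month/year of Day 1".
- **Guard on starts:** "If the end date is present, then the imputed start date will be set to the end date" when the imputed start would fall after it. No other check is written.
- **End, same month and year as the event start:** "then the date will be set to the date of the event start date".
- **End, other cases:** "missing days will be imputed as the day component of the event start date" and "missing months/years will be imputed as the month/year of the event start date", with the treatment start date as fallback.

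The section assumes that an event with an incomplete end date was over by the day the form was completed, but no step applies this as a cap.

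The completed dates are then used in two places. SAP 5.3.1 uses onset dates to decide treatment emergence and tabulates TEAEs "based on the treatment taken at AE start date". SAP 5.3.3 decides concomitant status by the same section: "Missing end dates will be imputed as previously outlined in" Section 3.3.5.

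**The concern.** The start rule would suit a trial with one treatment period. Here placebo subjects move to active drug at Week 6, and all subjects are re-randomised 1:1 to stay on active or go to placebo at Week 12 (SAP 1.1 and 3.2). A date tied only to the first dose in Period 1 can therefore change whether an event counts as treatment-emergent and which treatment it is counted under.

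The SAP takes account of periods elsewhere. SAP 3.3.4 imputes dosing dates period by period, and SAP 3.3.6 bounds visit windows by the Period 2 and Period 3 randomisation dates. The AE and medication date rule does not. It has no floor at first dose, no check that the date exists or lies within the study, and no requirement that an end date follow its start.

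**Working it through.** The documents give no figure on this point, so there is none to reproduce. The rule was applied literally to example dates and then enumerated.

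**Inputs.** Nominal periods: Period 1 is study days 1–42, Period 2 is 43–84, Period 3 is 85–126, and Week 22 follow-up is day 154. Study day follows SAP 3.3.7. Assumptions: Day 1 ranges over every date from 12 June 2018 (Protocol Version 1.3, SAP 3.2) to 25 March 2020 (enrolment stop, SAP 1.1); onset is uniform over days 1–126; no end date is recorded, so the cap does not act.

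**Example dates**

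| Result | Known facts | Date under the rule |
|---|---|---|
| Non-existent | Day 1 31 Jan 2019; onset Feb 2019 | 31 Feb 2019 |
| Non-existent end | Start 31 Jan 2019; end Feb 2019 | 31 Feb 2019 |
| Pre-dose | Day 1 15 Nov 2019; onset 10 Jan, year missing (10 Jan 2020 is study day 57) | 10 Jan 2019, study day −309 |
| Off study | Day 1 15 Nov 2019; onset 2020, no end date | 15 Nov 2020, study day 367 |
| Wrong period, backward | Day 1 1 Feb 2019; onset Mar 2019 (days 29–59; 15–31 March, 17 of 31 days, is Period 2) | 1 Mar 2019, day 29, Period 1 |
| Wrong period, forward | Day 1 28 Jan 2019; onset Apr 2019 (days 64–93; 1–21 April, 21 of 30 days, is Period 2) | 28 Apr 2019, day 91, Period 3 |
| End before start | Start 20 Dec 2019; end 10 Jan, year missing | 10 Jan 2019 |
| Medication end too early | Start 1 March, stop March, Day 1 20 March | 1 March: prior only, though 12 of the 31 possible stop dates (20–31 March) are on or after Day 1 |

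**Enumeration of start dates by what is missing**

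- *Day only.* No date exists for 1.3% of onsets. None is pre-dose or beyond Week 22. Of Period 1 onsets, 4.5% move to Period 2. Of Period 2 onsets, 14.6% move back to Period 1 and 19.4% forward to Period 3. Of Period 3 onsets, 2.4% move to Period 2. Wrong period overall: (4.5 + 14.6 + 19.4 + 2.4)/3 = 13.6%.
- *Day and month (year-only).* Onsets in Day 1's calendar year are set to Day 1: 81% of Period 2 and 68% of Period 3 onsets. The remaining 19% and 32% fall in the next calendar year and land off study.
- *Year only missing.* 19% become pre-dose.
- *Month only missing.* 36% become pre-dose if the same-month rule needs a recorded month and year, and 0% if it also applies after the month has been filled in. The text allows both readings.

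**Period error versus treatment error.** Assume 1:1:1 allocation, 1:1 re-randomisation and no dropout. A swap between Periods 1 and 2 changes treatment only for placebo-start subjects (1/3). A swap between Periods 2 and 3 changes it for the half who go to placebo. For day-only gaps:

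- active-time onsets counted under placebo: (14.6/3 + 19.4/2)/3 = 4.9% of onsets;
- placebo-time onsets counted under active: (4.5/3 + 2.4/2)/3 = 0.9%.

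For year-only onsets all set to Day 1, in weeks of onset time per randomised subject:

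- active time credited to placebo: 1/3 × (6 + 6/2) = 3 weeks;
- placebo time credited to active: 2/3 × (6/2) = 2 weeks.

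**The case against.** **A reader might infer that the rule systematically sends events to Period 1 and so favours the drug in one direction.** The documents do not support that. Day-only gaps move more Period 2 onsets forward to Period 3 than back to Period 1. Year-only onsets of active-start subjects later withdrawn to placebo are credited to active drug. Nor are all year-only events of placebo-start subjects counted as placebo: those in the next calendar year land off study. What remains is that, under the assumptions above, the two directions do not cancel exactly. More active time is credited to placebo than the reverse.

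**The end-date cap.** It removes off-study starts when a complete on-study end date exists. It does not help ongoing events, and it does not address pre-dose or non-existent dates.

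**Medication start dates.** SAP 5.3.3 sends only medication end dates to Section 3.3.5, and ongoing medications always count as concomitant. The medication point is therefore confined to end dates.

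**Few partial dates are likely.** Subjects are asked about AEs about every two weeks (Protocol 5.1.3–5.1.5) and eCRFs are source-verified (Protocol 8.1). Complaints are recorded by study period (Protocol 6.1), so the period may be known even when the date is not. These points stand and keep the severity low.

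**Existing checks.** Listings show partial dates as recorded (SAP 8), and results are verified by independent programming (SAP 5). That should expose 31 February, but the SAP does not say what to put in its place. A plausible wrong date would pass, because both programmers would apply the same rule.

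**Conservatism.** Setting a same-month onset to Day 1 counts it as treatment-emergent, which is cautious for TEAE counts. That is true, but it does not settle which treatment the event belongs to.

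**Conclusion.** The point holds as a minor defect. Taken literally, SAP 3.3.5 gives wrong results for some patterns and does not merely lack detail:

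- non-existent dates when Day 1 or the event start falls on the 29th to 31st;
- pre-dose dates when the year is missing across a year end, and on one reading when only the month is missing;
- off-study starts for year-only onsets in the next calendar year with no recorded end;
- wrong-period attribution;
- end dates that are too early.

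Pre-dose and off-study starts need a missing month or year; a missing day alone does not cause them. Treatment attribution errs in both directions. The percentages rest on uniform onset, nominal period lengths and the assumed Day 1 range, and each applies only to records with that pattern of missing parts. The documents do not say how many there are. Safety analyses are descriptive, so no hypothesis test depends on this. What could change is a small number of entries in the TEAE and concomitant medication tables.

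**What to change.** Replace the start and end rules in SAP 3.3.5 before database lock:

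1. **Start.** Compare the known parts with the first-dose date of each period. Use the earliest valid calendar date compatible with them, floored at Day 1 unless the known parts or the end date show earlier onset.
2. **Ambiguous period.** Prespecify one rule for a month or year that spans a period change. Add a sensitivity tabulation that assigns ambiguous events to active treatment. Assigning every such event to active would be a directional choice, so it serves better as the sensitivity analysis than as the main rule.
3. **End.** Use the last valid day of the known month or year, capped at form completion or last contact, and never before the start.
4. **Traceability.** Flag every imputed record and report the number by pattern of missing parts, so that the reader can judge the effect.

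The cost is one SAP paragraph and a macro change. The downside is that slightly more events may count as treatment-emergent and slightly more medications as concomitant.
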